7.1 Screening Visit (within 30 days of Day 1 injection)

- Obtain signed informed consent for study participation
- Preliminary review of inclusion and exclusion criteria
- Allocation of unique subject number; this number will be used to document the subject data in the case report forms (CRFs) and enrollment log
- Interview including the following subject-specific characteristics:
 - Demographic data - date of birth, gender, race
 - Medical/surgical history - all relevant prior medical and surgical conditions will be recorded in the CRF. Documented medical conditions will also note the month and year of onset if the condition is still active.
 - Concomitant Medications (within 30 days before Day 1 injection).
- Vital signs (body temperature, heart rate, blood pressure, and respiratory rate after at least 1 minute in a resting position).
- Electrocardiogram (ECG); subjects will either have a normal ECG or an abnormal ECG deemed not clinically significant by the PI.
- Blood draw for routine hematology, chemistry, serum pregnancy test for women of child-bearing potential. Females of child bearing potential are defined as women that are not surgically sterile (hysterectomy or bilateral oophorectomy) nor postmenopausal for at least 1 year prior to screening. Women who are not of childbearing potential will not require a pregnancy test.
- Urine collection for routine urinalysis.
- Physical examinations will include assessment of height and weight and an examination of general appearance, skin, eyes, ears, nose, throat, head and neck (including thyroid), lungs, heart, abdomen, lymph nodes, musculoskeletal, and nervous system. Any clinically relevant finding is to be documented as a baseline finding. Physical exams that are conducted as standard of care prior to signing informed consent may be used if they are performed within 30 days of injection.
- Assessment of edema/lymphedema, utilizing a pitting edema scale as provided in [Appendix 3](#), will be performed.
- KS history and classification.
- KS Lesion Assessment:
 - Cutaneous KS evaluation: All cutaneous lesions will be identified, documented, and photographed during the screening exam. Photographs will be collected per the photography protocol currently in use within the Department of Dermatology at UCSF, as provided in [Appendix 4](#).

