7.2 Day 1 (IV Injection)

7.2.1 Before Injection

- Assessment of adverse events
- Concomitant medication review
- A negative urine pregnancy test for women of child-bearing potential within 48 hours of injection.
- Final check of inclusion/exclusion criteria
- Vital signs (body temperature, heart rate, systolic and diastolic blood pressure, and respiratory rate within 30 minutes prior to investigational product injection, after at least 1 minute in a resting position)

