7.5 Day 7 ± 3 (IV Injection)

7.5.1 Before Injection

- Follow-up assessment from SC injection including changes in concomitant medication and adverse events
- A negative urine pregnancy test for women of child-bearing potential within 48 hours of injection.
- Final check of inclusion/exclusion criteria
- Vital signs (body temperature, heart rate, systolic and diastolic blood pressure, and respiratory rate within 30 minutes prior to investigational product injection, after at least 1 minute in a resting position)

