8.6 Safety

8.6.1 Adverse Events

8.6.1.1 Definition of Adverse Event

The definitions below follow International Conference on Harmonization (ICH) – Good Clinical Practice (GCP) (see also ICH Guideline for Clinical Safety Data Management: Definitions and Standards for Expedited Reporting).

Adverse Event (AE)

An AE is defined as any untoward medical occurrence in a subject administered a pharmaceutical product and which does not necessarily have a causal relationship with this treatment. An AE can therefore be any unfavorable and unintended sign (including an abnormal laboratory finding), symptom, or disease temporally associated with the use of a medicinal (investigational) product, whether or not considered related to the medicinal (investigational) product.

Any clinically significant change in a condition (worsening) from screening that results in a change in subject management will be considered an AE and will be recorded on the AE page of the CRF.

By definition for this study, all untoward medical occurrences beginning on the day of Visit 2 Baseline (Day 1) through the Follow-up Phone Call are to be reported as AEs. AEs continuing after study completion will be followed to normalization or stabilization. Additionally, untoward medical events occurring prior to the day of Tc 99m tilmanocept administration will be collected and added to the subject's medical history unless they are related to a study procedure, in which case the event will be recorded as an AE. SAEs will be reported from the time of consent through the end of participation.

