8.6.2.3 Vital Signs

Vital signs comprise the measurement of body temperature, heart rate, respiration, and systolic and diastolic blood pressure. All measurements will be taken after the subject has been in a resting position for at least 1 minute.

Vital signs will be measured at screening and within 30 minutes before investigational product injection, and within 30 minutes post-injection.

Any clinically significant change from screening (worsening) that results in a change in subject management will be considered an AE and will be recorded on the AE page of the CRF.

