10.1053/j.semnuclmed.2013.04.008. Review. PubMed PMID: 23905617.

Appendix 1 Schedule of Events – Cohorts 1 and 2

Evaluation	VISIT 1 Screening Days -29 to 0	VISIT 2 Pre- and Post-IV Injection Day 1		Follow-up Phone Call (Day 7±3)
		0:00	60-75 Minutes	
Informed Consent	x			
Entry Criteria	x			
Medical History	x			
Vital Sign Assessment	x	x ^{be}		
ECG	x	x ^e		
Physical Examination	x ^c			
Assessment of Edema/Lymphedema	x			
Photography of all KS Cutaneous Lesions	x			
Review of Medications	x	x		x
Clinical Laboratory Evaluation: Chemistry, Hematology, UA	x		x ^d	
Serum Pregnancy Test	x	x ^a		
Tilmanocept Administration		x		
Whole Body Planar and Whole Body SPECT/CT Imaging			x	
Biopsy of Non-Visceral Lesion			x ^d	
Adverse Event Monitoring	x	x	x	x

[figure not shown]
- a. Urine pregnancy test must be completed and determined to be negative in women of childbearing potential within 48 hours of injection.
- b. Time point 0:00 is before Tilmanocept administration (a 30 minute pre- and post injection window is permitted for vital signs).
- c. Physical examinations done within 30 days of injection may be used even if conducted prior to obtaining informed consent if they are ordered and conducted at the direction of the Investigator as part of his/her standard of care.
- d. Labs and biopsy will be completed at the conclusion of the 60-75 minute post-injection scan.
- e. ECG and vital signs must be within 30 minutes post-injection.

Appendix 2 Schedule of Events – Cohort 3

Evaluation	VISIT 1 Screening Days -29 to 0	VISIT 2 Pre- and Post-SC Injection Day 1			VISIT 3 Pre- and Post-IV Injection Day 7 ± 3	7 ± 3 Day Post-IV Follow-up Phone Call
		0:00	60-75 Minutes	4-6 Hours	0:00	60-75 Minutes
Informed Consent	X					
Entry Criteria	X					
Medical History	X					
Vital Sign Assessment	X	X ^{be}			X ^{be}	
ECG	X	X ^e			X ^e	
Physical Examination		X ^c				
Assessment of Edema/Lymphedema	X					
Photography of all KS Cutaneous Lesions	X					
Review of Medications	X	X			X	X
Clinical Laboratory Evaluation	X			X ^d		X ^d
Serum Pregnancy Test	X	X ^a			X ^a	
Tilmanocept Administration		X			X	
Whole Body Planar and Optional SPECT/CT Imaging			X	X		X
Biopsy of Non-Visceral Lesion						X ^d
Adverse Event Monitoring	X	X	X	X	X	X

- a. Urine pregnancy test must be completed and determined to be negative in women of childbearing potential within 48 hours of injection.

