(mean, standard deviation, minimum, median, maximum, range, n) on the raw values as well as their changes from pre-injection on Day 1 (and Day 7 [\pm 3] for Cohort 3) will be presented by dose group and overall. Time points included in this analysis are Day 1 (and Day 7 [\pm 3] for Cohort 3) within 30 minutes pre-injection and within 30 minutes post-Injection. If repeat vital signs are taken at a given time point, then the last measurement will be used for the analysis tables. A shift table will be created showing shifts Abnormal/Abnormal, Abnormal/Normal, Normal/Abnormal, Normal/Normal from pre-injection to post-injection of Tc 99m tilmanocept. This analysis will be performed by dose group and overall.

All vital signs will be listed, including those not presented in the analysis tables.

Physical Exams

A complete physical exam will be performed during screening. A data listing of the physical exam results will be created as shown in [Appendix B](#).

Concomitant Medications

All concomitant medications will be coded with WHO Drug Dictionary (Uppsala Monitoring Centre) version March 2017 or later. A data listing will be constructed with Preferred Term, Verbatim Term, ATC Level 1 Code, and ATC Level 4 Code. A summary table will be provided to show the counts and percentages of subjects taken medications by ATC Level 4 Code and Preferred Term by dose group and overall.

Clinical Laboratory Parameters

Changes in hematology, clinical serum chemistry and urinalysis between screening (i.e., baseline) and the post-injection time point will be calculated, and descriptive statistics will be calculated on the raw and change from baseline values by dose group and overall. A copy of the normal laboratory values for all laboratories utilized for this study will be submitted to the Sponsor (or designee) prior to initiation of the study. A shift table will be created showing shifts Abnormal/Abnormal, Abnormal/Normal, Normal/Abnormal, Normal/Normal from screening baseline to post-injection of Tc 99m tilmanocept. This analysis will be performed by dose group and overall.

ECG

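### The vital-sign AE rule compares post-injection readings with screening, while the SAP compares them with the same-day pre-injection reading: a minor inconsistency in safety classification

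*Protocol*

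**What the plan says.** Protocol 8.6.2.3 schedules three readings: "Vital signs will be measured at screening and within 30 minutes before investigational product injection, and within 30 minutes post-injection". Its AE sentence then uses only the first of them: "Any clinically significant change from screening (worsening) that results in a change in subject management will be considered an AE". Section 8.6.1.1 has a matching sentence for conditions in general, "Any clinically significant change in a condition (worsening) from screening", with the same requirement that management changes.

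The pre-injection reading is a fixed part of every injection visit. Protocol 7.2.1 places it "within 30 minutes prior to investigational product injection", and 7.4.1 and 7.5.1 do the same for the two Cohort 3 injections.

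The SAP takes the other reference. Section 5.0 summarises vital signs "on the raw values as well as their changes from pre-injection on Day 1", and does likewise for the Cohort 3 IV visit. The vital-sign shift table runs from pre-injection to post-injection, and the Table 22 shell labels the pre-injection row as baseline.

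The documents also define treatment emergence differently. Protocol 9.5.4 uses the date and time of injection; SAP 5.0 uses the date of first administration only.

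**The concern.** The post-injection reading is there to show what happened after the injection. The natural comparator is the value from minutes earlier, which the protocol collects and the SAP uses. The AE sentence passes over it for a reading from another day, so the rule and the analysis can classify the same three numbers differently.

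Two consequences follow from a literal reading. A subject whose pressure is well above screening before injection, and who drops sharply afterwards to about the screening level, shows no worsening from screening. That event is then an AE only if the investigator turns to the general definition. In the other direction, a subject already worse than screening on arrival can meet the rule on Day 1 before any drug is given, provided the change is clinically significant and alters management.

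This deserves attention because only an AE can become an ADR. The ADR proportion is the primary endpoint (Protocol 9.2), and under 5.3 one ADR among the four Cohort 1 subjects adds two more subjects.

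**Working it through.** **1. Age of the reference.** Appendix 1 gives "VISIT 1 Screening Days -29 to 0", and Protocol 7.1 allows screening within 30 days of the Day 1 injection. Protocol 7.5 puts the Cohort 3 IV injection on Day 7 ± 3, that is Day 4 to Day 10.

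- Oldest screening reading at Day 1: 1 − (−29) = 30 days, which matches the stated window.
- Check on the day count: IV on Day 10 plus a call 10 days later is Day 20, and 20 − (−29) + 1 = 50 days, which matches the limit in Protocol 3.4.
- Screening reading at the Cohort 3 IV injection: from 4 − 0 = 4 days to 10 − (−29) = 39 days old.
- Pre-injection reading: at most 30 + 30 = 60 minutes before the post-injection one.

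**2. The two rules on one set of readings.** Invented systolic values: screening 118, pre-injection 148, post-injection 116 mmHg.

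| Rule | Reference | Change |
|---|---|---|
| Protocol 8.6.2.3 | screening | 116 − 118 = −2 mmHg |
| SAP 5.0, Table 22 | pre-injection | 116 − 148 = −32 mmHg |

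The first gives no worsening to speak of; the second is a large acute fall.

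**3. A worsening present before injection on Day 1.** Protocol 8.6.1.1 collects AEs from the day of Visit 2, so an event found that morning before dosing can be recorded as an AE. Protocol 9.5.4 would not count it as treatment-emergent, because its start time precedes the injection. The SAP's date-only definition would count it.

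**4. How much noisier the screening reference is (illustration only).** The documents give no standard deviations and no numerical threshold. Assume a 20 mmHg fall in systolic pressure as the cut, a day-to-day SD s_d of 8 to 12 mmHg, a within-visit SD s_w of 4 to 6 mmHg, and normal errors.

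- SD of change against pre-injection: √2 × s_w = 5.7 to 8.5 mmHg.
- SD of change against screening: √(2(s_d² + s_w²)) = √(2(64 + 16)) = 12.6 to √(2(144 + 36)) = 19.0 mmHg.
- Probability of crossing the cut when the true fall is μ: Φ((μ − 20)/SD).

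| True fall | Against pre-injection | Against screening |
|---|---|---|
| 30 mmHg | 88% to 96% | 70% to 79% |
| 0 mmHg | 0.02% to 0.9% | 6% to 15% |

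With s_d widened to 6 to 14 mmHg, a true 30 mmHg fall fails to cross the cut 16% to 32% of the time against screening and 4% to 12% against pre-injection. With no true fall, the cut is crossed 2.5% to 18% of the time against screening and under 1% against pre-injection.

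The expected change is the same against either reference; only its variance differs. These are rates of crossing an assumed cut, not rates of AEs or ADRs.

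**The case against.** The strongest reply is that 8.6.2.3 adds a trigger and does not close the list. Section 8.6.1.1 counts any untoward sign linked in time to the product as an AE, and makes every untoward event from Day 1 to the follow-up call reportable, with no comparison to screening. An AE assessment sits in the same 0 to 30 minute window as the post-injection vital signs. In the example above, whether a return to the screening level is untoward is a clinical judgment. If it is, the general definition covers it. The −32 mmHg enters the SAP change summary either way, and every reading is listed in Data Listing 14. All of this stands.

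The reply on drift also stands. Ordinary day-to-day variation does not become an AE under 8.6.2.3, because the change must be clinically significant, a worsening, and followed by a change in management. To reach the primary endpoint it must also be a noxious response for which a causal link cannot be ruled out (Protocol 5.3). SAP 5.0 further says that events before administration go to medical history. However, Protocol 8.6.1.1 sends only events before the day of administration there, so the Day 1 case remains open.

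It can also be said that an AE judgment and a descriptive table may use different references without contradiction, and that screening is the SAP baseline for laboratory values and ECG. That is fair for those two, which have no scheduled pre-injection measurement. For vital signs a better reference is already collected. The specific and general rules can also give different answers for one event, and the text does not say which prevails.

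**Conclusion.** The inconsistency is real and minor. It rests on the text and the day count alone: a reference up to 30 days old, or 39 for the Cohort 3 IV injection, where one at most an hour old is available and used by the SAP. It concerns the classification of events, not whether they are captured.

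A reader might infer that acute falls will be missed, that routine drift will be recorded as AEs, or that the ADR endpoint and escalation are distorted. The documents do not support these readings. The general definition and the pre/post tables still show acute changes, the conditions in 8.6.2.3 filter out routine drift, and the step from AE to ADR needs a causal judgment. One subject in a cohort of four is 25%, so a single reclassified event would count, but nothing in the documents allows its probability to be estimated. Nor does the screening reference dilute the average effect. It makes the comparison noisier, and the size of that noise in the illustration depends on the assumed SDs and the assumed 20 mmHg cut.

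**What to change.** - In Protocol 8.6.2.3, and by a matching sentence in 8.6.1.1, state that post-injection vital signs are compared with the pre-injection reading of the same visit. In Cohort 3 this applies separately to the SC and the IV injection. This brings the AE rule into line with SAP 5.0.
- Keep screening as the reference only for changes found before injection.
- In SAP 5.0, define treatment emergence by date and time, as Protocol 9.5.4 does, so that a change already present before the Day 1 injection is not treatment-emergent.

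The cost is two sentences in the protocol and one in the SAP. No measurement is added: the pre-injection reading is taken at every injection, and Protocol 8.6.1.3 already requires the date and time of AE onset.

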8.6.2.4 Clinical Laboratory Parameters for Screening and Safety

Clinical laboratory tests to be evaluated in this study include hematology, serum chemistry, and urinalysis. Clinical laboratory tests will include the following as defined in Table 2.

Table 2. Clinical Laboratory Parameters

Hematology	Leukocytes, hemoglobin (Hgb), hematocrit (HCT), neutrophils, eosinophils, basophils, lymphocytes, monocytes, red blood cells (RBC), platelets
Serum chemistry	Aspartate aminotransferase (AST), alanine aminotransferase (ALT), alkaline phosphatase, total bilirubin, creatinine, chloride, potassium, sodium, total protein, albumin, globulin, carbon dioxide (CO ₂), blood urea nitrogen (BUN)
Urinalysis	pH, specific gravity

The site laboratory will provide the necessary supplies to collect the blood and urine samples.

All laboratory reports must be promptly reviewed for clinical significance by the investigator, and upon review, initialed and dated by the investigator.

Good clinical practice would suggest that a copy of the laboratory results also be provided to the subject's referring physician.

Any change in a laboratory value, which results in a change in subject management (additional controls or treatment required), will be reported as a clinically significant change. Clinically significant changes in laboratory parameters, which are not the result of laboratory error, are to be recorded as AEs.

Any clinically significant changes in laboratory values are to be followed up with repeated tests at appropriate intervals (as determined by the investigator) until the values return to baseline level or until the abnormality is explained by the investigator.

The expected amount of blood to be withdrawn is shown in [Table 3](#).

Table 3. Approximate Amount of Blood Withdrawn

Time point of examination	Amount of blood taken
Laboratory examination (Screening)	10 mL
Laboratory examination (Post-IV Imaging)	10 mL
Laboratory examination (Post-SC Imaging: Cohort 3 only)	10 mL
Total	20 mL (Cohort 3: 30 mL)

9 STATISTICAL METHODS

The study is a prospective, open-label, single-center, dose escalation, comparative, safety study of injected Tc 99m tilmanocept in the detection of and assessment of localization to cutaneous KS or non-cutaneous focus (visceral or other, e.g. CNS [central nervous system]) in HIV-positive subjects with active KS by planar and SPECT/CT imaging. The dose escalation portion of the study is a 4+2 design with no dose de-escalation. The statistical objective of the study is to determine the maximum tolerated dose (MTD) of Tc 99m tilmanocept and to compare the capabilities of Tc 99m tilmanocept to localize in cutaneous and non-cutaneous sites of KS. A study center is defined as a treatment administration site or cohort of treatment administration sites under the control and supervision of the same PI.

9.1 Randomization Methods

The study is not randomized.

9.2 Safety Variables

The primary variable for this study is the presence or absence of an ADR during the subject's participation in the trial following Tc 99m tilmanocept injection. The primary safety endpoint will be computed as the proportion of subjects with an ADR.

9.3 Efficacy Variables

The efficacy variables for this study are as follows:

- Nuclear medicine specialist determination of presence/absence of illumination (i.e., localization positive/negative, anatomic site) relative to background from SPECT imaging results for each subject;
- Clinically identified presence/absence of KS (based on any previous diagnostic evaluations);
- Quantitative SPECT gamma counts for each biopsied lesion.

The efficacy endpoints for this study are as follows:

- Per subject localization rate of Tc 99m tilmanocept in at least one KS suspected or confirmed lesion by planar and/or SPECT/CT imaging
- Per lesion/region concordance of Tc 99m localization with anatomical areas of active KS defined by confirmed diagnosis or clinical symptomology
- Localization intensity for each biopsied and clinically defined lesion as determined by quantitative SPECT gamma counts
- Per biopsied lesion proportion of CD206-expressing cells and total CD206 as determined by histology and relative IHC fluorescence
- Per lesion/region concordance of IV vs SC Tc 99m localization with anatomical areas of active KS defined by confirmed diagnosis or clinical symptomology.
- Per subject localization rate of Tc 99m tilmanocept in areas other than KS by planar and/or SPECT/CT imaging

- Per area localization rate of Tc 99m tilmanocept in the most frequently identified areas other than KS by planar and/or SPECT/CT imaging

A localized subject is one for whom Tc 99m by planar and/or SPECT/CT imaging results in the illumination of at least one site relative to background as determined by the nuclear medicine specialist.

A localized KS lesion is a lesion that is both clinically identified or suspected KS and planar or SPECT/CT illuminated.

Localization in areas other than KS will also be defined per subject and per area, where these areas are clinically negative KS locations based on clinical symptomology.

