	
administration of 200 µg/ 5 mCi Tc 99m tilmanocept approximately one week apart. At least one subject enrolled into each cohort must meet inclusion criteria 4c, as defined above (suspected non-cutaneous or confirmed non-cutaneous KS). For determination of the primary endpoint, a review meeting for safety will be held after the completion of each cohort prior to opening the next dose cohort. Cohorts will be dosed per the following table:
 

	Tc 99m tilmanocept Dose	Route of Administration	Number of Subjects	

Cohort 1	100 µg/ 5 mCi	IV	n = 4	

Cohort 2	100 µg/ 10 mCi	IV	n = 4	

Cohort 3	200 µg/ 5 mCi	IV and SC	n = up to 6	

 
Following IV administration, all subjects will have a whole body planar scan with optional SPECT/CT region of interest scanning beginning at 60-75 minutes post-injection. Subjects in Cohort 3 will additionally have a whole body planar scan with optional SPECT/CT region of interest scanning beginning at 60-75 minutes and 4-6 hours following SC injection.
		Tc 99m tilmanocept Dose	Route of Administration	Number of Subjects	Cohort 1	100 µg/ 5 mCi	IV	n = 4	Cohort 2	100 µg/ 10 mCi	IV	n = 4	Cohort 3	200 µg/ 5 mCi	IV and SC	n = up to 6
	Tc 99m tilmanocept Dose	Route of Administration	Number of Subjects														
Cohort 1	100 µg/ 5 mCi	IV	n = 4														
Cohort 2	100 µg/ 10 mCi	IV	n = 4														
Cohort 3	200 µg/ 5 mCi	IV and SC	n = up to 6														

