7.7 Imaging and Acquisition of Imaging Data

Imaging will be a whole body planar scan followed by optional SPECT/CT region(s) of interest scan beginning at 60-75 minutes post-IV injection (all Cohorts) and 60-75 minutes and 4-6 hours post-SC injection (Cohort 3 only).

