4.2 Analysis of Efficacy Variables

Localization in KS Sites

The number and percentage of subjects with at least one biopsy-confirmed or clinically suspected KS lesion that has localized with Tc 99m tilmanocept by planar and/or SPECT/CT imaging will be computed. A 95% exact confidence interval on the per-subject localization rate will be computed. This analysis will be performed by dose group and route of administration.

Per-lesion/region localization of Tc 99m tilmanocept by planar and/or SPECT/CT imaging will be computed across all biopsy-confirmed or clinically suspected KS lesions of all subjects. A 95% exact confidence interval on the per-lesion/region localization will be calculated. This analysis will be performed by dose group and route of administration.

An analysis table will also be provided to display the counts of KS lesions localized by imaging that were not previously identified clinically.

Concordance between IV and SC tilmanocept in biopsy-confirmed or clinically-suspected KS lesion sites will be assessed with a cross-tabulation of the IV and SC findings, including the joint probability distribution. The sampling unit for this analysis will be the site. An exact conditional version of McNemar's test will be performed to test the hypotheses

$$H_0: \pi_{IV} = \pi_{SC}$$
$$H_A: \pi_{IV} \neq \pi_{SC},$$

where π_{IV} and π_{SC} represent the probabilities of localization with IV (only) tilmanocept and SC (only) tilmanocept, respectively. In addition, the number and proportion of subjects with concordance and reverse concordance of observed sites of discrete localization of Tc 99m tilmanocept following IV and SC localization will be summarized.

Localization Intensity by Planar and/or SPECT/CT Imaging

Tc 99m tilmanocept average pixel intensity and percent above background will be summarized with descriptive statistics (mean, standard deviation, minimum, median, maximum, and range) for each biopsied lesion localized on imaging following IV injection of Tc 99m tilmanocept by dose group. Summary statistics will be presented separately by imaging type (planar, SPECT/CT).

Proportion of CD206-expressing Cells

Per biopsied-lesion proportion of CD206-expressing cells as determined by histology and IHC fluorescence will be summarized by descriptive statistics (mean, standard deviation, minimum, median, maximum, and range) by dose group.

Localization in Non-KS Sites

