6.3 Subject Imaging

Each subject will undergo whole body planar imaging. SPECT/CT imaging of region(s) of interest is optional for each subject. Results of all imaging procedures will be listed.

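### SPECT/CT is optional with no selection rule, but localization counts a positive on either modality and the tables do not separate them, so unequal SPECT/CT use could look like a dose or route difference

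*Protocol*

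**What the plan says.** **Who is imaged how.** The protocol synopsis states that after IV injection "all subjects will have a whole body planar scan with optional SPECT/CT region of interest scanning". Protocol 7.7 describes "a whole body planar scan followed by optional SPECT/CT region(s) of interest scan", and SAP 6.3 states that "SPECT/CT imaging of region(s) of interest is optional for each subject". Neither document gives a criterion for doing the optional scan or for choosing its regions. The two schedules disagree: Appendix 1 (Cohorts 1 and 2) has the row "Whole Body Planar and Whole Body SPECT/CT Imaging", while Appendix 2 (Cohort 3) has "Whole Body Planar and Optional SPECT/CT Imaging".

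**Localization.** Protocol 9.3 and SAP 1.1.1 treat a lesion as localized if planar or SPECT/CT illuminates it. SAP 4.2 defines the subject-level count by a KS lesion "that has localized with Tc 99m tilmanocept by planar and/or SPECT/CT imaging will be computed", analysed by dose group and route. The shells for Tables 5 to 9, 14 and 15 have no modality split, and Listing 18 has no modality column. The protocol is not uniform here: 9.3 takes the illumination variable from SPECT results, and 9.5.3 computes subject-level non-KS localization from SPECT, where the SAP allows planar, SPECT/CT or both.

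**Intensity.** Protocol 9.3 lists the variable "Quantitative SPECT gamma counts for each biopsied lesion" and the endpoint "Localization intensity for each biopsied and clinically defined lesion as determined by quantitative SPECT gamma counts". SAP 4.1 keeps SPECT gamma counts but limits them to lesions localized after IV injection. SAP 4.2 instead analyses average pixel intensity and percent above background, separately for planar (Table 10) and SPECT/CT (Table 11).

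**The concern.** Under an either-modality rule, a lesion in a region that also gets SPECT/CT has two chances to be called positive, and a lesion elsewhere has one. Protocol 3.2 says SPECT/CT is there for better resolution, so it may change a reading. With no rule for its use, the share scanned can differ between cohorts, between the IV and SC visits in Cohort 3, and with how much uptake the planar scan shows. A difference in scanning would then be reported as a difference in localization.

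Two results are exposed: the localization rates set side by side by cohort, and the exact McNemar test of IV against SC, the only hypothesis test in the SAP. The reader could not undo the mixing from the planned output, because the tables and Listing 18 do not say which modality produced a positive. The conflict between the appendices adds to this. Read literally, SPECT/CT use would differ between Cohorts 1 and 2 and Cohort 3, which is one of the dose contrasts.

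**Working it through.** **The plan's own figure.** The planned total is 4 + 4 + up to 6 = up to 14 subjects, which reproduces. The documents give no SPECT/CT use, no planar detection rate and no gain from SPECT/CT, so the inputs below are assumptions shown as ranges.

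**Inputs (assumed)**
- p: share of lesions detected on planar, 0.3 to 0.7
- q: share of planar-negative lesions that SPECT/CT turns positive, 0.2 to 0.6
- f: share of lesions in regions given SPECT/CT
- McNemar level 0.05 two-sided, since no alpha is stated, with sites treated as independent

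**Step 1: false difference between two groups with the same p and q.** The either-modality rate is p + (1 − p)·q·f. The difference between groups is (1 − p)·q·(f1 − f2). For a 50-point gap in SPECT/CT use, in percentage points:

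| p | q = 0.2 | q = 0.4 | q = 0.6 |
|---|---|---|---|
| 0.3 | 7 | 14 | 21 |
| 0.5 | 5 | 10 | 15 |
| 0.7 | 3 | 6 | 9 |

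The ends of the range are 0.3 × 0.2 × 0.5 = 0.03 and 0.7 × 0.6 × 0.5 = 0.21. If one group is fully scanned and the other not at all, the range doubles to 6 to 42 points. If f1 = f2 or q = 0, it is zero. On planar reads alone f drops out and the false difference is zero, provided the planar call does not depend on the SPECT/CT images.

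**Step 2: the IV-versus-SC test.** Take p = 0.5 and q = 0.4, with SPECT/CT done after one route only.
- *Identical planar results for both routes.* Every discordant site then points the same way, with probability (1 − 0.5) × 0.4 = 0.2 per site. Six discordant sites are needed to reject: 2 × 0.5^6 = 0.031, whereas 2 × 0.5^5 = 0.063. The chance of six or more, a false rejection, is 0.02 with 12 sites, 0.57 with 30 and 0.99 with 60.
- *Planar reads independent between routes.* The chance is 0.06, 0.26 and 0.53. With no SPECT/CT effect (q = 0) it would be 0.01, 0.03 and 0.03.

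This is the extreme case of one-sided use, and the number of sites is also assumed.

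**Step 3: intensity.** Only the SPECT/CT summary (Table 11) needs the optional scan. If each subject has a 50% chance of SPECT/CT, a cohort of 4 has at most one scanned subject, and so no standard deviation, with probability (1 + 4) × 0.5^4 = 0.31. At 25% and 75% the figures are 0.74 and 0.05. For a cohort of 6 the three figures, at 25%, 50% and 75%, are 0.53, 0.11 and 0.005. Table 10 is not affected.

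**The case against.** The strongest reply has four parts.

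- **Intensity is largely covered.** A reader might infer from Protocol 9.3 and SAP 4.1 that a subject without SPECT/CT drops out of the intensity analysis. The documents do not support that, because SAP 4.2 and Table 10 summarise planar intensity for localized biopsied lesions. Nor does route enter, since intensity is analysed after IV injection only. A reader might also infer that the complete-case rule (Protocol 9.5.5; SAP 2.3) governs missing SPECT counts. It is worded for primary efficacy variables, whereas the primary endpoint is adverse drug reactions and intensity is secondary. This part stands.
- **The second chance is not proven.** SPECT/CT follows the planar scan over chosen regions, so it may mainly characterise uptake already seen and convert few negatives. The documents do not settle this. It limits the size but leaves the mechanism open.
- **Precision is low and most results are descriptive.** No test between cohorts is planned. In a cohort of 4 the subject-level rate moves in 25-point steps, and the two-sided exact 95% interval for 4 of 4 is 0.40 to 1.00. A false difference of a few points could show only at lesion level. This stands for the cohort tables, but the McNemar p-value is inferential.
- **Some information is already listed.** Listing 16 has a SPECT/CT start time for each subject, so who was scanned is visible. It does not show which positives came from SPECT/CT, and Listing 18 does not either.

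It would also go too far to say that SPECT/CT is compulsory in Cohorts 1 and 2. Appendix 1 omits the word optional, but the body text and SAP include it. The documents contradict each other and do not establish either reading.

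**Conclusion.** The concern holds for localization. The plan fixes neither who gets SPECT/CT nor how its findings are separated from planar ones, so unequal use can pass into the cohort tables and the IV-versus-SC test. Whether it will, and by how much, cannot be known from the documents. The 3 to 21 points rest on assumed detection and conversion rates and a 50-point gap in use. The false-rejection rates rest further on the assumed number of sites, independence of sites and one-sided scanning. None is an estimate for this trial.

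For intensity, what remains is a mismatch between the named endpoint (SPECT gamma counts) and the specified analysis (planar and SPECT/CT separately). All of this concerns secondary endpoints, and the primary safety endpoint is untouched. It is worth correcting because the correction is cheap.

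**What to change.** 1. Keep the protocol's either-modality endpoint. Add a planar-only version of Tables 5, 6, 8, 9, 14 and 15, and base cohort and route comparisons, including the McNemar test, on that same-modality version. Show the number of subjects and regions with SPECT/CT for each cohort and route.
2. Add a modality column to Listing 18 and split Table 7 by modality.
3. Align the intensity endpoint in Protocol 9.3 and SAP 4.1 with SAP 4.2 and Tables 10 and 11. Name planar percent above background as the measure available for every localized biopsied lesion seen on planar.
4. Reconcile Appendix 1 with Appendix 2 and the body text on whether SPECT/CT is optional, and reconcile the SPECT-only wording in Protocol 9.3 and 9.5.3 with the SAP.

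**Cost.** No scan is added. The work is extra table rows or columns and recording the modality of each read, and the planar-only rate may be lower than the either-modality rate. Items 1 and 2 need only SAP and shell edits plus that recording. Items 3 and 4 touch protocol text, and Protocol 3.3 requires an amendment for any change that is not purely administrative.

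**What it leaves open.** SC has two imaging times and IV has one. A planar-only Table 9 does not remove that imbalance, which needs its own rule.
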